1 BACKGROUND AND RATIONALE

1.1 Introduction

The optimal management of chronic obstructive pulmonary disease (COPD) is important at population and health system levels due to substantial costs, morbidity and mortality. At the individual patient level, experiencing shortness of breath, often on a daily basis, with periods of worsening symptoms, can have a big impact on quality of life, productivity, and outcomes. Inhaled medications are the most effective therapies for symptom relief and available for COPD patients—particularly when given in combination. (GOLD 2017) Inhaled therapies are available as metered dose inhalers (MDI), soft-mist inhalers (SMI), dry powder inhalers (DPI), and by nebulization. Although DPI's are breath-actuated and tend to be easier for patients to use than the MDI or SMI, there is emerging evidence that delivery from DPI and drug stability of the powder is suboptimal in some patients and settings. It has recently been shown that COPD patients can exhibit suboptimal inspiratory rates during exacerbations in the hospital ([Loh, Sharma](#)) as well as in the outpatient setting ([Sulaiman 2017a, Jansenns](#)); it is unclear what impact this may have on the efficacy and safety of DPIs. Several population-based studies from the United Kingdom report that a DPI (Diskus® inhaler), with relatively low respirable mass (portion delivered into target airways) and larger particle size is associated with greater COPD exacerbation frequency and oropharyngeal side-effects compared to inhalers with a higher respirable mass in both COPD and asthma patients. ([Price, Jones, Dekhuijzen](#)) Although published evidence regarding suboptimal delivery from DPIs in the COPD population is emerging, substantial knowledge gaps exist, including peak inspiratory flow in ambulatory COPD patients when clinically stable and during periods of worsened respiratory symptoms. This specific knowledge gap is the principal basis of our investigation.

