4.2 Study Visits

There will be six study visits/encounters over a 22-26 week period as shown in the Study Procedures and Assessments Table. Two study visits will occur at the UNC Clinics (Visits 1 and 2)

and four visits will only involve a telephone interview of subjects by study personnel (Visits 3, 4, 5, and 6).

Visit 1- Screening Visit

At Visit 1, after obtaining written informed consent, a clinical history will be obtained from the patient and if the subject meets all inclusion and exclusion criteria, a CAT score will be determined. The patient will undergo PIFR assessment based on prescribed DPI. PIFR will be recorded with best approximation to nearest 1 L/min. Subjects will be excluded if PIFR > 90 L/min based on Ellipta® and Diskus® setting or inability to achieve minimum PIFR for prescribed DPI setting (< 30 L/min for Handihaler®, < 60 L/min for Ellipta®, Diskus®, or Inhub®). The PIFR will be performed in triplicate by the patient at the recommended device setting (based on patient's DPI specific internal resistance) in the physical position (e.g. sitting) that the patient normally uses to self-administer their inhaler(s). Further, they will be instructed to perform the PIFR consistent based on the manufacturer instructions for proper DPI inhalation technique (e.g. Ellipta®, Diskus® DPI, , Inhub®) "Breathe out gently and breathe in steadily and deep"). For the Handihaler®, subjects will be instructed as follows – "Breathe out completely in one breath. Empty your lungs of air. Breathe in deeply until your lungs are full." If the patient meets the inclusion and exclusion criteria including a PIFR < 90 L/min, they can proceed to Visit 2 (Enrollment) either during the same encounter or scheduled within 30 days. If there is greater than 30 days between Visit 1 and 2, another informed consent will be reviewed and signed.

For inclusion, historical spirometry is required to be documented to ensure patients meet the GOLD definition of COPD using airflow obstruction. Most recent spirometry data will be used for characterization of the enrolled cohort. No spirometry testing will be performed as part of this study.

Visit 2- Enrollment Visit

- A physical examination including measurement of waist circumference (measured in inches horizontally through the narrowest part of the torso, between the lowest rib and the iliac crest)
- Medical history (includes exacerbations history)
- COPD medication use (maintenance and reliever)

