- Patient-reported outcomes (PROs)
 - CAT score (COPD Assessment test)
 - mMRC score (modified Medical Research Council)
 - mBorg score (modified Borg dyspnea score)

- PIFR measurement in three different physical positions – sitting, standing, and lying tilted at 45° with head forward. (repeated using PIFR setting for each DPI patient is receiving)
- Pre- and post-bronchodilator PIFR measurement in sitting position
- Subject instructed on proper use of PIFR device and recording of PIFR measurement and modified Borg dyspnea score using the provided Study Notebook
- Subject instructed to mail PIFR and modified Borg dyspnea score on a monthly basis to the research team using supplied self-addressed, stamped envelopes

Visits 3, 4, 5, and 6 - Telephone Visits

At Visits 3, 4, 5, and 6 (at 4, 8, 12 , and 24 weeks after Visit 2 -permissible ± 2 week window for each visit), study personnel will contact the participant by telephone to obtain PIFR and symptom questionnaires recordings during the preceding 2 weeks. A time period less than 2 weeks is acceptable if the subject had mailed in their monthly log recently. PIFR measurements and respiratory symptom questionnaires (modified Borg dyspnea score only) will have been recorded by study participants using a Study Notebook. PIFR will be recorded for each DPI the patient is receiving. A CAT score, mBorg, and mMRC will also be determined by study personnel as part of each visit. Ascertainment of exacerbations, medication adherence, and change in inhaler regimens will be completed. In part, the telephone visit will be undertaken to increase subject's compliance to study procedures.

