5.1.4.1 Efficacy Evaluation (if applicable)

Changes in PIFR and dyspnea (modified Borg) that occur in the COPD population in the home setting during periods of stable respiratory symptoms and periods of worsening will be measured and recorded by participating subjects. PIFR measurements, PRO (mMRC, modified Borg, CAT) will also be undertaken in the research clinic setting. PRO will also be completed with each telephone-based study visit.

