- We will use mixed models to explore associations of monthly PIFR averages over time and clinical and demographic factors. Subjects will be considered as random factor, other variables will be considered fixed effects.
- Association of PIFR with CAT score, mBORG score and mMRC
 - Association of PIFR and CAT scores at V1, V3, V4, V5, V6 (for PIFR, use the measurement in the week of each telephone follow-up, or the month average)

- Correlation of change in CAT scores with change in PIFR from baseline after 24 weeks
- Association of PIFR and mBORG score at V2, V3, V4, V5, V6
- Association of PIFR and mMRC scores at V1, V3, V4, V5, V6 (for PIFR, use the measurement in the week of each telephone follow-up, or the month average)

For COPD exacerbation analyses, the proportion of patients with COPD exacerbations (from Kaplan Meier curve) and the rate of exacerbations occurring during follow-up will be reported along with 95% CI. A patient will be considered censored for exacerbations at the time of the last documented visit, the end of the study, the switching of device (between medium and high resistance DPI) or death (whichever occurs earlier), if they did not experience an exacerbation before. The exacerbations will be reported overall and stratified by severity. The associations between exacerbations and PIFR will be explored in different ways, for all exacerbation, stratified by severity of exacerbations, and stratified by device.

- The rate of exacerbations and sPIFR will be analyzed with negative binomial models (or another model if more appropriate).
- For patients with exacerbations, the mean of PIFR in the week before, of, and after each exacerbation will be calculated and reported.

All tests with p value < 0.05 will be interpreted nominally as statistically significant.

Missing data

- No imputation for PIFR
- No imputation for COPD exacerbations
- No imputation for CAT, mBORG and mMRC

Sample Size and Power

In this application, we propose to recruit 120 COPD participants for study enrollment. There are several rationales for this sample size selection.

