16 APPENDIX 1. STUDY PROCEDURES AND ASSESSMENTS

Visit number	V1 ^a	V2	V 3,4,5,6
Procedures and assessments	Screening Visit	Enrollment Visit	Telephone Follow-up Visits
Target time(s) and allowable time frames		At same time as or within 1 month of Screening Visit	At 4, 8, 12, 24 weeks after V2 (± 2 weeks)
Informed consent	X		
Clinical history	X	X	
Prior medication history	X	X	
Inclusion and exclusion criteria	X	X	
Physical examination including waist circumference		X	
Vital signs measurement		X	
Peak Inspiratory Flow Rate (Performed in triplicate at resistance of all DPIs the patient is receiving)	X	Pre- and post-bronchodilator (albuterol) Perform PIFR in three positions (sitting, standing, and lying at 45° angle with head tilted forward) [#]	Done 3x/wk. (each session in triplicate with highest value recorded) at home by patient after enrollment [#] (Daily during worsened symptoms)
COPD Assessment Test score (CAT) questionnaire	X	X	X
Modified Borg Dyspnea Score (mBorg)		X	X Done 3x/wk at home by patient after enrollment
Modified Medical Research Council questionnaire (mMRC)		X	X
COPD exacerbation history*	X	X	X
COPD medication use and adherence	X	X	X

^aMild, moderate and severe exacerbations will be defined as:

Mild – doubling use of inhaled rescue medication ≥ 48 hours and not meeting definition of moderate or severe; Moderate – increased rescue medication and oral corticosteroid, not requiring hospitalization; Severe – hospitalization for exacerbation

[figure not shown]
PIFR will be performed before performing spirometry (if spirometry is performed at that visits) using InCheck Dial settings for each DPI patient is receiving

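### Section 6.3 places the PIFR-mMRC association at a visit where mMRC is not collected, and leaves 48 to 72 of about 72 scheduled home PIFR-mBorg pairs per patient out of any planned association

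*Combined protocol and SAP*

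**What the plan says.** **Analysis plan.** Section 6.3 lists "Association of PIFR and mMRC scores at V1, V3, V4, V5, V6" and "Association of PIFR and mBORG score at V2, V3, V4, V5, V6". The CAT and mMRC lines carry a rule for choosing the PIFR value: "for PIFR, use the measurement in the week of each telephone follow-up, or the month average". The mBorg line carries none.

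**Collection at visits.** In section 4.2 the only patient-reported outcome at Visit 1 is CAT: "if the subject meets all inclusion and exclusion criteria, a CAT score will be determined". Visit 2 collects CAT, mMRC and mBorg. Visits 3 to 6 are telephone calls at which staff determine all three scores and also obtain the home recordings of the preceding two weeks. Section 5.1.2 adds only CAT at Visit 1. The mMRC row of Appendix 1 is blank at V1 and marked at V2 and at V3 to V6.

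**Collection at home.** At Visit 2 patients are instructed in "recording of PIFR measurement and modified Borg dyspnea score using the provided Study Notebook". Section 4.1 has both recorded on Monday, Wednesday and Friday when stable and daily when the patient judges symptoms to be worse. Section 7 agrees. Appendix 1 gives daily recording during worsening for PIFR, but lists home mBorg at three times a week only.

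**Stated purpose.** Section 5.1.4.1 says that changes in PIFR and dyspnea "in the home setting during periods of stable respiratory symptoms and periods of worsening will be measured".

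**The concern.** There are two separate defects. The first is a contradiction: the mMRC association is assigned to a visit at which mMRC does not exist and omits a visit at which it does. With no imputation, a programmer following section 6.3 literally has no baseline mMRC pair for anyone.

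The second is an omission. The home log puts PIFR and mBorg on one schedule, in the setting the protocol says it wants to study. The mBorg association is nevertheless tied to five visits. At four of them there is no clinic PIFR, the staff-determined mBorg is separate from the home session, and the PIFR to be paired is undefined. A handful of visit points mainly shows whether more breathless patients have lower PIFR. It says little about whether a given patient's PIFR falls when that patient is more breathless, which the repeated home pairs could show. An unstated rule also leaves the pairing to be chosen after the data are seen, while section 6.3 reads p < 0.05 as nominally significant.

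**Working it through.** **The plan's own figure.** The documents give no count of PIFR-symptom pairs. Their one sample-size figure reproduces: n = 1.96² x 0.40 x 0.60 / 0.088² = 119.05, rounded up to 120. This point does not depend on it except as the number of patients.

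**mMRC, side by side.**

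| Source | V1 | V2 | V3-V6 |
|---|---|---|---|
| Section 6.3 (analysis) | yes | no | yes |
| Section 4.2 (visits) | CAT only | yes | yes |
| Section 5.1.2 | CAT only | yes | yes |
| Appendix 1, mMRC row | blank | yes | yes |

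The three collection sources agree with each other; the analysis list differs from all of them.

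**Scheduled home pairs per patient** (sessions per week from section 4.1, duration from the synopsis):

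- 3 x 24 = 72 with full completion and one DPI.
- Over the 22 to 26 week span in section 4.2: 3 x 22 = 66 to 3 x 26 = 78.
- Ceiling if both were recorded every day for 24 weeks: 7 x 24 = 168.

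**Pairs in the planned mBorg analysis.** There are at most 5 per patient, so 5 x 120 = 600, against 72 x 120 = 8,640 scheduled home pairs. If diary completion were 60% to 80% (an assumption; the documents give no figure), the home total would be 0.6 x 8,640 = 5,184 to 0.8 x 8,640 = 6,912.

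**How many home pairs go unused.** Let k be the home pairs that each of the four calls draws from the log. Unused = 72 - 4k.

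| Reading of the mBorg line | k | Unused per patient |
|---|---|---|
| mBorg determined during the call; no home pair used | 0 | 72 |
| One home session per call | 1 | 68 |
| One week of sessions | 3 | 60 |
| The full preceding two weeks | 6 | 48 |

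**What this means for precision (illustration on assumed autocorrelation).** The standard error of a pooled within-patient correlation in 120 patients is about 1/√(120 x (m - 1) - 1), where m is the effective number of pairs per patient.

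- m = 5, treated as independent: 1/√479 = 0.046.
- m = 72, independent sessions: 1/√8,519 = 0.011.
- 72 sessions with a product of lag-1 autocorrelations of 0.64: m = 72 x 0.36/1.64 = 15.8, giving a standard error of 0.024.

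The home pairs would cut the standard error by a factor of 1.9 to 4.2 under these assumptions. The gain is far smaller than the raw 72-to-5 ratio, because sessions within a patient are correlated.

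**The case against.** The mMRC discrepancy may be only a label. V1 and V2 can be the same encounter, so V1 may be a slip for V2 and no data need be lost. That stands as a limit on its weight. But the visits can also be up to 30 days apart, or longer with renewed consent, and the text must name the visit that holds the score.

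On mBorg, the parent line in section 6.3 and the synopsis mention the association without limiting it to visits, staff retrieve recent home recordings at each call, and V2 has PIFR and mBorg together. Same-session pairs could therefore enter. This also stands, and it is why the unused number is a range. It does not supply a pairing rule, and even the most generous reading leaves 48 of 72 pairs out. The existing mixed model does not fill the gap, because it relates monthly PIFR averages to clinical and demographic factors.

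A reader might go further in three ways that the documents do not support:

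- *Worsening short of an exacerbation never enters an analysis.* It does. Every home PIFR reading feeds the primary endpoint, the other sPIFR endpoints, the descriptive PIFR analyses and the monthly averages. Section 6.3 also reports mean PIFR around each exacerbation, and mild exacerbations need no steroid, antibiotic or admission.
- *The visit points come mostly from stable periods.* Nothing in the documents shows this.
- *The notebook has no mark for a worsened day.* The notebook form is not among the appendices, so its fields are unknown. Dated entries off the Monday-Wednesday-Friday schedule would in any case identify some worsened days.

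Finally, the objectives and endpoints list symptom associations and PIFR around exacerbations, not a stable-versus-worsened comparison, and the home sampling first serves the primary endpoint. For mBorg, omission is therefore the fair description.

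**Conclusion.** The point holds in two parts. The mMRC visit list contradicts the collection schedule and cannot be followed at baseline. The mBorg association lacks a pairing rule at four of its five time points, and 48 to 72 of about 72 scheduled home pairs per patient have no planned association with PIFR. Unused here means not related to PIFR; mBorg is still summarised descriptively.

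The figure of 72 assumes 24 weeks, full completion and one DPI. A second DPI adds device-specific pairs and missed entries remove them. Whether worsening adds pairs is unsettled, because Appendix 1 differs from sections 4.1 and 7 on home mBorg during worsening.

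All of this is exploratory. It does not bear on the primary endpoint, its confidence interval or N=120. It is worth correcting before analysis because the data are already planned and PRO associations are a named exploratory objective.

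**What to change.** 1. **mMRC:** in section 6.3 change V1 to V2, giving V2 to V6. State which V2 PIFR is used, since that visit measures three positions and pre- and post-bronchodilator values.
2. **mBorg at visits:** keep the planned analysis and add a pairing rule, as for CAT and mMRC. Say whether the score at V3 to V6 is the one determined on the call or the one in the log, and choose one of the two PIFR options (the week's measurement or the month average).
3. **Home pairs:** add, by device setting, a mixed model of all same-session pairs with a patient random effect: PIFR = β0 + βB x (patient mean mBorg) + βW x (session mBorg - patient mean) + patient effect + error. Report βW with its 95% CI as the within-patient slope. Allow for serial correlation between sessions.
4. **Schedule:** reconcile Appendix 1 with sections 4.1 and 7 on home mBorg during worsening, because this decides whether worsened-day pairs exist.

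The cost is a few lines of analysis-plan wording, one schedule correction and one further exploratory model. Items 1 to 3 need no new data collection.

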4.4 Concomitant Medication documentation

All COPD medications within 30 days of study enrollment and during the 24 week study period will be recorded.

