4.6 Subject Completion/ Withdrawal procedures

If a patient decides to withdraw for any reason our contact information will be provided and they can email any member of the research team. If participants have a change in their prescribed DPI during study, study procedures will continue using previously prescribed DPIs and noting prescription changes.

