6.2 Exploratory Endpoints

PIFR Endpoints:

1. Time to first occurrence of sPIFR (in days)
2. Number and proportion of sPIFR
3. Rate of sPIFR, defined as the number of sPIFR / number of days in the study, multiplied by 30 as sPIFR/month.

Exacerbation Endpoints:

Occurrence (yes/no), number, severity (mild, moderate, severe) and rate of COPD exacerbations over 24 weeks. Mild, moderate and severe exacerbations will be defined as:

1. Mild – doubling use of inhaled rescue medication > 48 hours and not meeting definition of moderate or severe
2. Moderate – increased rescue medication and either oral corticosteroid or antibiotics, not requiring hospitalization
3. Severe – hospitalization for exacerbation

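### The overall 24-week exacerbation proportion is censored at a medium/high-resistance DPI switch, although the endpoint does not depend on the DPI and exacerbations are still ascertained afterwards (exploratory endpoint, minor weight)

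*Combined protocol and SAP*

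**What the plan says.** Section 6.2 lists the exploratory exacerbation endpoint as "Occurrence (yes/no), number, severity (mild, moderate, severe) and rate of COPD exacerbations over 24 weeks". Mild, moderate and severe events are defined by rescue medication use, oral corticosteroid or antibiotic treatment, and hospitalization. None of the three definitions mentions a DPI or a resistance class.

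Section 6.3 takes the proportion of patients with exacerbations from a Kaplan-Meier curve. Event-free patients are censored at the earliest of several times. Besides the final visit on record and study end, these include "the switching of device (between medium and high resistance DPI) or death (whichever occurs earlier), if they did not experience an exacerbation before". The next sentence reads "The exacerbations will be reported overall and stratified by severity". Associations with PIFR are then to be explored "for all exacerbation, stratified by severity of exacerbations, and stratified by device". No separate censoring rule is given for the overall, severity-specific or device-stratified figures.

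A switch does not end participation. Under section 4.6, after a change of prescribed DPI, "study procedures will continue using previously prescribed DPIs and noting prescription changes". Section 4.2 says of the telephone visits: "Ascertainment of exacerbations, medication adherence, and change in inhaler regimens will be completed". Appendix 1 also lists exacerbation history for Visits 3 to 6.

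**The concern.** An exacerbation after a change of device class is a valid event under section 6.2 and will have been asked about. The Kaplan-Meier rule discards it if it is the patient's first. The plan states no reason for this, no target limited to time on the original device class, and no sensitivity estimate that ignores the switch.

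Readers would take the overall figure as the share of patients with an exacerbation in 24 weeks. Censoring at a switch recovers that share only if switchers have the same exacerbation risk as comparable patients still at risk and the switch does not alter it. If switchers are at higher risk the figure is too low; if at lower risk, too high. The documents give neither reasons for switching nor its frequency, so the direction cannot be known in advance.

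**Working it through.** **The plan's own figure.** Section 6.3 gives no number for the exacerbation analysis. Its only precision figures are for sPIFR, and they serve here as a yardstick for size. For a proportion p and half-width d, n = 1.96² × p(1−p)/d². At p = 0.40 and d = 0.088 this is 3.8415 × 0.24/0.007744 = 119.1, rounded up to 120, as in the plan's table. All 15 cells of that table reproduce. Conversely, at N = 120 and p = 0.40 the half-width is 1.96 × √(0.24/120) = 8.8 points.

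**Inputs.**
- From the documents: N = 120 and 24 weeks (168 days).
- Assumed: base 24-week proportion 40% (the pilot sPIFR figure, borrowed only as an example); share f of patients with a potential switch time 5-20%, times uniform over 24 weeks; hazard ratio (HR) in switchers 0.5-3; constant hazards.

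**Model with the HR acting only after the switch.** The cumulative hazard over 24 weeks is H = −ln(0.60) = 0.5108. Everyone has the same hazard before a switch, so the switch-censored Kaplan-Meier value stays at 40%. Averaged over switch times, the 24-week event-free probability of a switcher is

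S = (e^(−H) − e^(−H·HR)) / (H × (HR − 1)), and S = 0.60 at HR 1.

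The proportion with all follow-up counted is (1 − f) × 0.40 + f × (1 − S). Bias is 0.40 minus that value.

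Worked case, HR 3 and f = 20%: S = (0.600 − 0.216)/(0.5108 × 2) = 0.3759. Full follow-up gives 0.8 × 0.40 + 0.2 × 0.6241 = 0.4448. Bias = −4.5 points.

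| HR | S | Bias, f = 5% | Bias, f = 10% | Bias, f = 20% |
|---|---|---|---|---|
| 0.5 | 0.6836 | +0.4 | +0.8 | +1.7 |
| 1 | 0.6000 | 0 | 0 | 0 |
| 2 | 0.4698 | −0.7 | −1.3 | −2.6 |
| 3 | 0.3759 | −1.1 | −2.2 | −4.5 |

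**First events left out.** As a share of all patients this is f × [(1 − e^(−H))/H − S], where (1 − e^(−H))/H = 0.40/0.5108 = 0.783. At f = 5% and HR 0.5 it is 0.5% (0.6 of 120). At f = 5% and HR 3 it is 2.0% (2.4 of 120). At f = 20% and HR 3 it is 8.1% (9.8 of 120). At HR 1 it is 0.9% to 3.7%: events are dropped, but without bias.

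**Other model forms.** If the HR applies to switchers from day 0, the range at the 40% base is +1.7 to −3.0 points. With a constant switching hazard in place of uniform switch times, and the HR after the switch, it is +1.7 to −4.6 points. The order of magnitude does not depend on the model.

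**Against sampling error.** With switch censoring, the Greenwood half-width at N = 120 and a 40% base is 8.9 to 9.3 points. Every bias above is smaller than that.

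**The case against.** The strongest defence is that the rule is a pre-specified choice. It estimates exacerbation occurrence while patients stay on their resistance class, in a study organised around resistance class. It matches the sPIFR rule. After a switch, home PIFR continues on the earlier DPI and may no longer describe the device in use. This is a plausible reason for results by device and for relating exacerbations to PIFR. It does not carry over to the overall figure: no such on-device target is stated, and section 6.2 says over 24 weeks.

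The size argument stands. The endpoint is exploratory and descriptive, only crossings between medium and high resistance count, and prescriptions must have been unchanged for four weeks before enrollment. Nothing in the documents supports 20% switching.

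It is also true that the revised figure would still be censored at death and at the last visit. This point leaves those parts of the rule alone.

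A reader might infer more than the documents support:
- *That post-switch exacerbations disappear from the report.* Only the Kaplan-Meier proportion is shown to lose them; the negative binomial analysis of rates has no stated switch cut-off.
- *That continued collection contradicts censoring.* The two are compatible; data can be collected and an analysis can stop earlier.
- *That the switch date will be missing.* Section 4.4 says "All COPD medications within 30 days of study enrollment and during the 24 week study period will be recorded", and regimen changes are asked about at each call. No text mentions a date, and calls are scheduled "At 4, 8, 12, 24 weeks after V2", but silence about a form field does not establish a gap.
- *That the primary sPIFR proportion has the same fault.* Its switch rule is written under the exploratory time-to-first analysis. sPIFR is defined against any prescribed DPI, so stopping at a switch has a possible reason there, and later readings may relate to a device no longer prescribed.

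**Conclusion.** The concern holds for one quantity: the overall Kaplan-Meier proportion of patients with exacerbations, with its split by severity. As written, the rule leaves out first events that the study collects, and the result equals the 24-week proportion only if switching is unrelated to exacerbation risk.

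Whether the result will be biased, and in which direction, cannot be told from the documents. The ranges shown are illustrations resting wholly on assumed switching, hazard ratio and base proportion; they are not bounds. Within them the effect is modest. It is nonetheless a shift in what is estimated, which the confidence interval does not cover. The sample size table is correct and concerns sPIFR. This is a minor point, worth making because the correction is cheap and needs no new data.

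**What to change.** In the exacerbation paragraph of section 6.3, remove the switch from the censoring rule for the overall proportion. Suggested wording:

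> For the 24-week proportion of patients with exacerbations, overall and by severity, event-free patients are censored at the last documented visit, the end of the study or death. A change between medium and high resistance DPI does not end follow-up. Device-stratified results, and one sensitivity estimate of the overall proportion, are also censored at the change. The number of patients with such a change will be reported.

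The cost is a wording change and one additional Kaplan-Meier estimate, using exacerbation data already planned. Visits and sample size do not change. The downside is that the overall figure will include time on another device class, so it describes patients rather than a device; the switch-censored sensitivity estimate shows how much that matters.
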